6.4 Post-Treatment/Follow-up Assessments

All subjects will be followed for a minimum of 30 days after the last dose of protocol therapy (genistein/placebo) to assess for AEs. If subjects complete all four cycles of anti-neoplastic therapy, this visit will occur at 35 ± 5 days following the last day of Cycle 4. If subjects are withdrawn or discontinued prior to completion of the anti-neoplastic therapy, this will occur at 35 ± 5 days following the last day the study supplement is administered.

All serious adverse events (SAEs), other grade 3 – 4 AEs that are believed to be related to the investigational intervention, cancer progressions and relapses (including date, description, and sites), secondary malignancies (including date, description, and sites), and deaths (with date and clinical narrative) must be reported until 6 months after the end of the study intervention. See [Section 9.2](#) for additional information on AE and SAE reporting during this period.

7 EVALUATION CRITERIA

7.1 Primary Endpoint

The primary endpoint of this clinical trial is the average day of neutrophil count recovery following myelosuppressive chemotherapy. Neutropenia will be defined as ANC < 500 cells/ μ l (grade 4 neutropenia per [CTCAE](#)), and the “day of recovery” for each subject during each cycle of chemotherapy will be defined as the first post-nadir day of each cycle that the ANC is \geq 500 cells/ μ l (i.e. \leq grade 3). For example, if the ANC is 400 cells/ μ l on Day 12 and 600 cells/ μ l on Day 14, then the day of recovery will be Day 14. For subjects whose ANC nadir is \geq 500 cells/ μ l, the day of recovery will be the day of the first ANC after their lowest ANC is obtained.

7.2 Secondary Endpoints (per cycle)

“Incidence” refers to both the frequency of an event per subject and the number of affected subjects in this study.

- **Severity of neutropenia**
- Duration of **grade 4 neutropenia during hospital admissions for febrile neutropenia**
- Frequency and duration of unplanned or prolonged **hospitalizations** due to (an) AE(s) ([Section 9.1.9](#))
- Days with **fever** (temperature > 101.5° F, or > 100° F more than once in a 24-hour period)
- Incidence and severity of **infections**
- Duration of **antimicrobial use**
- Duration and severity of oral **mucositis**
- Duration and severity of **peripheral motor neuropathy** (in subjects treated with vincristine)
- Incidence and severity of **hearing impairment** and **tinnitus** (in subjects treated with a platinum-based chemotherapy agent)
- Number of days of **delays and percent reduction of full planned doses of anti-neoplastic agents due to (an) AE(s)**
- Incidence of primary and secondary **G-CSF use**
- Number and cause of required **blood product transfusions**
- **Serum cytokine levels:**
 - G-CSF, granulocyte-macrophage colony stimulating factor (GM-CSF), interferon- α (IFN- α), IFN- γ , IL-1 β , IL-1 receptor antagonist (IL-1RA), IL-2 receptor (IL-2R), IL-4, IL-5, IL-6, IL-7, IL-8, IL-10, IL-12, IL-13, IL-15, IL-17, TNF- α .

- **Chemokines:** eotaxin, IFN- γ induced protein 10 (IP-10), monocyte chemotactic protein 1 (MCP-1), monokine induced by IFN- γ (MIG), macrophage inflammatory protein 1- α (MIP-1 α), MIP-1 β , Regulated upon Activation Normal T cell Expressed and presumably Secreted (RANTES).
- **Serum growth factor levels:** epidermal growth factor (EGF), fibroblast growth factor-basic (FGF-basic), hepatocyte growth factor (HGF), vascular endothelial growth factor (VEGF)
- **Serum CRP levels, homocysteine levels, and ESRs**

7.3 Toxicity and Safety

Toxicity will be assessed in subjects randomized to both groups for 30 days following the last dose of protocol therapy (genistein/placebo), as indicated in [Section 6.4](#). AEs will be graded using the [National Cancer Institute \(NCI\) Common Terminology Criteria for Adverse Events \(CTCAE\) Version 4](#). See also [Section 9](#).

8 STATISTICAL CONSIDERATIONS

8.1 Study Design

This is a multi-center, randomized, double-blind, placebo-controlled, stratified, two-arm trial with a cross-over component which results in both a between-group comparison (A vs B for Cycles 1 and 2 data) and a crossover within group difference comparison (genistein cycles minus placebo cycles data). Patterns of ANCs over time will be estimated and average day of recovery over the two cycles will be the primary comparison. Neutropenia is defined in [Section 7.1](#). For each subject, two co-primary endpoints will be estimated; a) the average day to recovery during Cycles 1 and 2, and b) the difference in the average days during genistein cycles and the average days during placebo cycles.

In addition, the study is designed to capture other clinically-relevant short-term side effects of therapy that appear to be reduced by genistein supplementation. Secondary endpoints are listed in [Section 7.2](#).

8.2 Sample Size and Accrual

This pilot study is designed to obtain preliminary data to describe the overall pattern of ANC over time during myelosuppressive chemotherapy, assess neutropenia, and to determine whether the data support a decrease in time to recovery of 3 days for the genistein group compared to placebo. Target sample size for this pilot study was based upon results from a chart review performed at UVA which found that the mean day of recovery for pediatric cancer patients receiving myelosuppressive chemotherapy was day 16.25. Group sample sizes of 22 eligible subjects per group achieves approximately 80% power to detect a difference of 3 days with a 5% one-sided Mann-Whitney-Wilcoxon Test. These results were based on 3000 Monte Carlo samples assuming a null Poisson (mean 16.25) distribution and an alternative Poisson (mean 13.25) distribution. ANC determination and neutropenia are defined in Sections 6.3 and 7.1. Adjusting for a 10% ineligibility/drop-out rate, approximately 49 - 50 subjects may need to be accrued to the study.

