3.1 Inclusion Criteria

- [1] Newly diagnosed solid tumor or lymphoma with histological verification
- [2] Age 1 - 21 years at time of diagnosis
- [3] Karnofsky/Lanksy performance score of ≥ 50
- [4] Able to tolerate enteral medication administration
- [5] Planned chemotherapeutic regimen for a patient must meet **all** of the following criteria:
 - a. A known myelosuppressive regimen which includes at least two of the following agents: actinomycin, carboplatin, cisplatin, cyclophosphamide, daunorubicin, doxorubicin, etoposide, ifosfamide, topotecan
 - b. At least four consecutive cycles
 - c. Cycle length is either 14 or 21 days
 - d. Regimen **must either alternate myelosuppressive chemotherapeutic agents in an X-Y-X-Y format**, such that the same chemotherapy is given every other cycle (e.g. vincristine/doxorubicin/cyclophosphamide | ifosfamide/etoposide), **or repeat the same chemotherapeutic agents each cycle in an X-X-X-X format** (e.g. repeated cycles of cisplatin/etoposide/bleomycin). Courses eligible for this trial may occur at any time during treatment provided that they are consecutive and follow the one of the described patterns. Non-myelosuppressive anti-neoplastic treatments will not be considered for the purposes of determining eligibility. Questions regarding whether or not a patient's chemotherapy plan meets inclusion criteria will be decided by the Study Chair.
- [6] Informed consent or parental permission and assent obtained prior to trial-related activities ([Section 4.3](#))
- [7] Able and willing to comply with all study related procedures
- [8] Women of childbearing potential must agree to use adequate contraception prior to study entry and for the duration of study participation. Should a woman become pregnant or suspect she is pregnant while participating in this study, she should inform her treating physician immediately.

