3.2 Exclusion Criteria

- [1] Known allergy to soy or any soy-based food or supplement
- [2] Unable or unwilling to discontinue consuming prohibited soy-based food or supplements while participating in this study ([Section 4.8.1](#))
- [3] Pre-existing neutropenia or neutrophil qualitative or quantitative disorder ([Section 6.3](#))
- [4] Pre-existing cytopenia or bone marrow failure syndrome
- [5] History of gastric or duodenal ulcers or hyperacidity syndromes
- [6] History of Human Immunodeficiency Virus (HIV)
- [7] Has an active infection requiring systemic therapy
- [8] Planned treatment does not include myelosuppressive chemotherapy
- [9] Enrolled on a therapeutic or supportive care clinical trial within the last 30 days
- [10] Current acute or chronic leukemia diagnosis
- [11] Requires medication dosing via an enteral feeding tube that terminates in the duodenum or jejunum. (Enteral feeding tubes that terminate in the stomach are acceptable for study medication delivery.)
- [12] Pregnant or breastfeeding woman
- [13] Incarceration
- [14] Secondary malignancy, i.e. the cancer for which the patient is presently or will be receiving treatment may not be a malignancy related to prior cancer therapy
- [15] Any condition which might be worsened by estrogen, such as breast cancer, uterine cancer, ovarian cancer, endometriosis or uterine fibroids
- [16] Any condition, in the investigator's opinion, that would compromise patient safety or study outcomes
- [17] Anyone who, in the investigator's discretion, would be unwilling or unable to comply with study procedures

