4.7.2 Genistein/Placebo Supplementation

For the purposes of this study, the duration of treatment cycles will coincide exactly with chemotherapy cycles. "Cycle 1" here refers to the first chemotherapy cycle during which the subject receives genistein or placebo, though this may not be the actual first cycle of the subject's chemotherapeutic treatment.

Subjects will receive 30 mg genistein (Arm A) or placebo (Arm B) daily throughout Cycles 1 & 2, beginning on the first day of the first cycle of chemotherapy coinciding with this study (Cycle 1 Day 1) and ending two days prior to the predicted start date of Cycle 3. Following a 2-day washout, subjects will then receive placebo (Arm A) or 30 mg genistein (Arm B) throughout chemotherapy Cycles 3 & 4, beginning on the first day of Cycle 3 and ending on the last day of Cycle 4. **The treatment schedule is summarized on Roadmaps, located in the Procedure Manual appendices.** For the purposes of this clinical trial, “study supplement” will refer to both genistein and placebo.

The study supplement will be delivered orally by the subject or a parent, and a diary will be kept to document dose administration. For doses given at home, subjects and parents will be instructed to bring unused pills to study visits. For children who are unable to swallow tablets, instructions for crushing and administering will be given to the families (Procedure Manual). Tablets may be crushed and delivered via feeding tube only if subjects are unable to take the medication orally and the feeding tube terminates in the stomach. Delivery to the duodenum or jejunum may alter genistein pharmacokinetics.

Subjects will record study treatments on a daily Pill Diary to indicate number of doses and time of dosing (Procedure Manual). If a subject misses a dose by less than 12 hours, he or she must be instructed to take the missed dose. If a subject misses a dose by more than 12 hours, he or she must be instructed to skip the missed dose and continue with regular dosing schedule. However, he or she must redose if vomiting occurs within the first 20 minutes after study supplement ingestion. Redosing may occur only once per 24 hour period.

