¹² CBC must be collected once during Baseline (Day -7 to 1), and then Day 1 of Cycles 2, 3, and 4, and Day 8 of Cycles 1, 2, 3, and 4. Once ANC begins to decrease each cycle, obtain twice a week until ANC recovery (see [Section 7.1](#) for definition of ANC recovery). CBC must include the following: hemoglobin, hematocrit, platelet count, total white blood cell count and automated differential (manual differential if automated not available).

¹³ Blood sample must be drawn at Baseline (Day -7 to Day 1), Day 1 of Cycles 2, 3, and 4, and the last day of Cycle 4.

¹⁴ Blood sample must be drawn on Day 1 of Cycles 1, 2, 3, and 4, and the last day of Cycle 4.

¹⁵ In subjects receiving platinum based chemotherapy only, an audiogram must be resulted at baseline (Day -7 to Day 1) and again 0 - 4 days prior to Day 1 of Cycles 2, 3, 4, and the last day of Cycle 4. If hearing loss is detected then adjust dose per [Section 4.7.4](#).

¹⁶ G-CSF, antimicrobials, blood product transfusions, anti-neoplastic agents, and soy-based products ([Section 4.8](#) and [6.4](#))

¹⁷ Concomitant medications used in the 28 days prior to the initiation of the study intervention

¹⁸ Dispense Day 1 of each cycle. Weekly review recommended but not required. Collect and review on the last day of each cycle.

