6.2 Pre-treatment Assessments

Informed consent will be obtained from a parent or guardian of eligible minor subjects, or the patient if ≥ 18 years old. Oral assent will be obtained from minor subjects ≥ 7 years old, unless more stringent requirements are imposed by a site's IRB. Consent and assent must be obtained prior to any study-related procedures. ([Section 4.3](#), Procedure Manual)

Subject eligibility must be confirmed prior to subject enrollment using the inclusion and exclusion criteria ([Section 3.1](#) – [3.2](#)). The following data must also be collected pre-treatment:

- Clinical data: diagnosis, stage, grade, site(s) of disease
 - Stage (extent of spread): *in situ*, localized, regional, distant, unknown
 - Grade (differentiation level): well differentiated/low grade, moderately differentiated/moderate grade, poorly differentiated/high grade, undifferentiated/highest grade
- Anticipated anti-neoplastic treatment regimen for courses coinciding with this trial: therapeutic agents (i.e. chemotherapy, hormonal therapy, immunotherapy, other small molecule inhibitors, gene therapy), doses expressed per kilogram body weight, duration of cycle (14 or 21 days), radiation dose and number of fractions (if applicable)
- Demographic data: date of birth, sex, race, and ethnicity
- Blood sample collection for serum homocysteine, C-reactive protein (CRP), and erythrocyte sedimentation rate (ESR), and complete blood count (CBC) with differential must be drawn at baseline (Day -7 to Day 1). Raw data will be reported.
 - CBC with differential must include hemoglobin, hematocrit, platelet count, total white blood cell count and automated white blood cell differential (manual differential if automated not available) (Procedure Manual).
- Medical history and physical exam for the purpose of establishing baseline conditions ([Section 6.2.1](#))
- Audiogram on Day -7 to Day 1 for subjects receiving platinum-based chemotherapy
- Use of the following concomitant medications in the 28 days prior to the anticipated Cycle 1 Day 1: G-CSF, antimicrobials, blood product transfusions, anti-neoplastic agents, and soy-based products. See [Sections 4.8](#), [6.3](#), and the Procedure Manual for additional details on concomitant medications.

In addition, the following **target AEs** must be assessed during the Pre-treatment Period. Use assessment closest to Cycle 1 Day 1 if more than one assessment is done during the Pre-treatment period.

- Neutropenia

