8.4 Data Analyses Plans

Graphical and repeated measure models will be used to describe the complete pattern of ANC over all four cycles. Between-group (Cycles 1 & 2) and crossover differences (Cycles 1 - 4) form the structure for treatment comparisons. Repeated measure models

will be used to assess differences in raw ANC, daily ANC, days with fever, duration of hospitalization, and duration of antimicrobial use for subjects admitted with febrile neutropenia. The Cochran–Mantel–Haenszel test statistics will be used in the analysis of stratified categorical data such as neutropenia grades (severe: ≤ 100 cells/ μl ; moderate: ≤ 500 cells/ μl ; mild: ≤ 1000 cells/ μl) and filgrastim (G-CSF) usage. For duration and severity of mucositis and peripheral motor neuropathy, detailed physical examinations will be documented at each weekly physical exam. Grading (grade 1 - 5) will be performed according to the [CTCAE](#) guidelines, version 4.0. The Cochran–Mantel–Haenszel test will be used to compare grade and repeated measure models for duration of mucositis between cycles containing genistein versus placebo.

Number of subjects who experience hearing impairment and tinnitus will be summarized by treatment for each cycle. The number of required blood product transfusions, both packed red blood cells and platelets, will be documented and compared during genistein and placebo cycles using repeated measure models. Reporting will be in the form of total ml/kg body weight infused of red blood cells and platelets. Criteria for transfusion are listed in [Section 4.8.2](#).

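### Co-primary (a) and the ANC and marker analyses have no prespecified adjustment for the baseline values the trial already collects; the gain in precision could be nil or useful, and adjustment costs almost nothing

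*Combined protocol and SAP*

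**What the plan says.** Section 8.1 states that "average day of recovery over the two cycles will be the primary comparison" and sets two co-primary endpoints: (a) average day to recovery in Cycles 1 and 2, compared between arms, and (b) the within-subject difference between genistein and placebo cycles. Section 8.2 gives 22 eligible subjects per group about 80% power to "detect a difference of 3 days with a 5% one-sided Mann-Whitney-Wilcoxon Test", assuming Poisson means of 16.25 and 13.25. No other test is named for day of recovery.

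Section 8.4 says repeated measure models "will be used to assess differences in raw ANC, daily ANC, days with fever" and other outcomes, without listing model terms. It does not mention CRP, ESR, homocysteine or cytokines, although objective 2.2.2 concerns serum markers of inflammation.

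The baseline data exist. Under section 6.2 the CBC with differential, CRP, ESR and homocysteine "must be drawn at baseline (Day -7 to Day 1). Raw data will be reported". Table 3 repeats this and puts the first cytokine sample on Cycle 1 Day 1.

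Three provisions bear on how much baseline ANC varies. Section 3.1 says "Courses eligible for this trial may occur at any time during treatment". Section 4.7.2 describes study Cycle 1 as the first supplemented cycle, "though this may not be the actual first cycle of the subject's chemotherapeutic treatment". Section 3.2 excludes "Pre-existing neutropenia or neutrophil qualitative or quantitative disorder". Randomization is stratified by cycle length only (section 8.3).

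**The concern.** Pre-Cycle 1 ANC is the starting value of the quantity from which day of recovery is derived. Subjects may enter untreated or after earlier chemotherapy, and nothing in the randomization balances that. With 22 per arm, a chance difference in baseline ANC passes into the Cycle 1-2 contrast in proportion to its correlation with the outcome. Any variance that baseline explains also stays in the error term.

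For the markers, baseline and follow-up are the same assay, which is the usual setting for ANCOVA, yet no analysis is written. If 8.4 stays open, the decision whether and how to adjust may be taken after the data are seen. In a trial of 44 that leaves room for a choice driven by the observed imbalance.

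**Working it through.** **Inputs from section 8.2.** 22 per arm; one-sided 5%; Poisson means 16.25 and 13.25; difference 3 days. Implied average SD = sqrt((16.25 + 13.25)/2) = sqrt(14.75) = 3.84 days.

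**Assumed input.** r, the correlation of pre-Cycle 1 ANC with day of recovery. The documents give no value, so it is ranged from 0 to 0.7.

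**Step 1: the plan's own figures.** With 40,000 simulated trials, the one-sided Mann-Whitney-Wilcoxon test has power 79.7% with continuity correction and 80.1% without. The stated 80% reproduces. As a cross-check, the normal approximation needs 21 per arm, and 21/0.955 (relative efficiency of the rank test) = 22.0. Accrual: 44/(1 - 0.10) = 48.9, which agrees with 49-50.

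**Step 2: variance.** Adjusting for one baseline covariate multiplies the variance by (1 - r²). Estimating its slope with 44 subjects costs a factor of about 1 + 1/40 = 1.025. Net factors:

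- r = 0.1: 0.99 × 1.025 = 1.015 (slightly worse)
- r = 0.2: 0.96 × 1.025 = 0.984
- r = 0.3: 0.91 × 1.025 = 0.933
- r = 0.5: 0.75 × 1.025 = 0.769

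**Step 3: power.** 6,000 simulated trials per value of r, with Poisson outcomes linked to a normal baseline by a normal copula and baseline as the only covariate:

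| r | Mann-Whitney-Wilcoxon | Rank ANCOVA | t test | ANCOVA |
|---|---|---|---|---|
| 0 | 79.9% | 79.5% | 81.7% | 80.7% |
| 0.1 | 79.6% | 79.3% | 81.4% | 81.1% |
| 0.2 | 80.0% | 80.6% | 82.0% | 82.7% |
| 0.3 | 78.9% | 81.7% | 81.3% | 83.5% |
| 0.5 | 80.2% | 88.2% | 82.8% | 90.1% |
| 0.7 | 80.7% | 95.4% | 82.4% | 96.9% |

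Simulated rejection under the null at r = 0.5 was 5.1% for both adjusted tests. Separate simulations of the same set-up differ by up to about two points. Taking all of them, ANCOVA and rank ANCOVA together span 78-81% at r = 0, 80-83% at 0.2, 82-84% at 0.3 and 87-90% at 0.5.

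Comparing like with like isolates the adjustment from the change of test. Rank ANCOVA minus Mann-Whitney-Wilcoxon is -0.4 points at r = 0, +0.6 at 0.2, +2.8 at 0.3 and +8.0 at 0.5. ANCOVA minus t test is -1.0, +0.7, +2.2 and +7.3.

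**Step 4: chance imbalance.** The standard error of the between-arm difference in a standardized baseline is sqrt(2/22) = 0.30 SD. An imbalance of that size moves the unadjusted estimate by r × 0.30 × 3.84 days: about 0.23 days at r = 0.2, 0.35 at 0.3 and 0.58 at 0.5, against a target of 3 days.

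**Step 5: markers.** The between-arm interval narrows by 1 - sqrt(1 - r²), before the cost of the covariate: about 5% at an assumed r of 0.3, 13% at 0.5 and 29% at 0.7. No marker correlation is given either.

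**The case against.** The strongest objection is that the size of the gain is unknown. Day of recovery is a calendar day and baseline ANC is a cell count, so the correlation of 0.5 often assumed for repeated measures of one variable has no claim here. The exclusion of pre-existing neutropenia cuts off the low end of baseline ANC. Entry part-way through treatment may widen the spread, and the net direction cannot be read from the documents. This stands: a reader might infer that the trial is certainly giving up 8 to 10 points of power, and the documents do not show that.

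Other stronger readings also fail:

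- *That the plan excludes baseline from the ANC models.* Section 8.4 lists no terms at all. That is silence, and baseline could enter as a first response or as a covariate.
- *That both co-primaries are affected.* Co-primary (b) compares each subject with themselves, so a stable effect of baseline ANC cancels.
- *That the test or the sample size is wrong.* Randomization keeps the unadjusted test valid, and the power reproduces. The test appears only in the power statement, and 8.4 does not confirm it as the final analysis.

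It is also fair to say that the Poisson variance may describe a single cycle, while the endpoint averages two. At an assumed between-cycle correlation of 0.5, averaging alone would multiply the variance by (1 + 0.5)/2 = 0.75. Power would then start higher and adjustment would add fewer points.

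Finally, ANC is not the only candidate covariate. Cycle length, as the randomization stratum, has at least as good a claim and belongs in the model.

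None of this removes the gap. The data are collected, no adjustment is specified, and prespecification is worthwhile whatever the correlation proves to be.

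**Conclusion.** The point holds as a low-cost improvement to the specification. It covers co-primary (a), the ANC repeated measure models and the Cycle 1-2 marker comparison. For co-primary (a) the gain is negligible at a correlation of 0.2 or less, about 2 to 3 points like for like at 0.3, and about 7 to 8 points at 0.5. The most it costs is about one point of power, at zero correlation. These figures rest on the plan's Poisson assumptions applied to the two-cycle average, an assumed correlation, and baseline ANC as the only covariate. The effect of adding cycle-length stratum was not simulated. Nothing here calls the 22 per arm or the stated 80% power into question.

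**What to change.** In section 8.4:

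1. Name ANCOVA, or rank ANCOVA to stay close to the test in 8.2, as the analysis of co-primary (a), with log pre-Cycle 1 ANC and cycle-length stratum as covariates.
2. Include log pre-Cycle 1 ANC as a covariate in the ANC repeated measure models.
3. Specify log-scale ANCOVA for the Cycle 1-2 marker comparisons, with the pre-supplement value as covariate.
4. Define baseline as a value drawn before the first dose of supplement. Day 1 values of Cycles 2 to 4 are post-randomization and should not serve as baseline.
5. Keep the unadjusted Wilcoxon test as a sensitivity analysis.

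The cost is a change of wording made before unblinding and one degree of freedom per covariate. No extra subjects, visits or samples are needed.
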